3.1.3 Exploratory Objectives

Exploratory objectives are:

- Compare the frequency of those subjects experiencing either component of a two-part composite endpoint consisting of DSA formation and the presence of TG ($cg > 0$) on centrally-interpreted institutionally-derived protocol (maintenance) biopsy and /or biopsy obtained for cause during the first year post-transplant.
- Examine the proportion with IA designation in subject groups at various thresholds of eGFR ($< 30, 40, \text{ and } 50 \text{ mL/min/1.73 m}^2$), and those with threshold of serum creatinine ($> 1.2 \text{ mg/dL}$) at one year.
- Assess and compare, between treatment groups, the association/correlation of the coefficient of variation (CV) and standard deviation (SD) of tacrolimus trough concentrations with each of the following: the composite endpoint of DSA and IA, DSA formation and IA individually, TG, ABMR, IFTA, renal dysfunction, various thresholds of eGFR ($< 30, 40, \text{ and } 50 \text{ mL/min/1.73 m}^2$), and the four components of the traditional composite endpoint.
- Summarize inpatient variability (IPV) by treatment group in subjects with at least three non-missing tacrolimus trough level assessments after the first six weeks following transplantation and on or before Day 365.

3.2 Study Design

This is an exploratory, two year, prospective, randomized, multi-center, open-label trial examining long-term kidney transplant outcomes through the use of an adaptive design and a two-part, composite surrogate endpoint. Specifically, it is designed to compare the effects of twice daily, immediate-release tacrolimus and once daily Astagraf XL on DSA formation and the development of a peripheral blood molecular profile indicating the presence of IA in de novo kidney transplant recipients during the first two years following transplantation. For the purposes of this study, IA will be defined as a positive molecular signature using the Transplant Genomics (TGI) Trugraf™ v.2.0 molecular assay (Transplant Genomics, Inc., Pleasanton, CA).

This study will enroll 550 living or deceased donor kidney transplant recipients, 16 to 70 years of age. Subjects will be screened prior to surgery and randomized 1:1 to receive immediate-release tacrolimus, administered twice daily, or Astagraf XL, as a component of a standard immunosuppression maintenance regimen also consisting of corticosteroids (complete steroid avoidance not allowed – steroid taper and withdrawal permitted if part of institutional protocol) and MMF (or Myfortic® equivalent). Investigators are encouraged to

start subjects on the randomized study treatment (immediate release tacrolimus or Astagraf XL) within 48 hours of transplantation (pre-transplant administration of study treatment is not allowed). However, if medically indicated per the treating physician's discretion, initiation of study treatment may be delayed for up to seven days post-transplant.

Given the variability of incidence rates for DSA reported in the literature, a stopping rule has been incorporated herein to mitigate the risk of continuing the study under incorrect prior assumptions relating to the true incidence rate of DSA formation (Section 4). To apply the rule, the incidence rate of the primary endpoint in the control group will be examined once 50% of control subjects have completed one year of therapy. Early termination of the study, or extension to a second year, will be predicated on this assessment (see Section 7.9).

Induction therapy is required for all participants, and will be administered (dosing, type of agent) per center protocol. Intravenous corticosteroids will be administered prior to revascularization as part of the initial induction regimen, with dose and duration of therapy also determined by the participating transplant center's standard protocol. Thereafter, subjects will be followed for up to two years during the open-label study period.

Initial pre-transplant cross-matching (XM) will be performed per local protocol. Initial XM serum will be collected and stored centrally to facilitate the later assessment of pre-formed antibody on an as needed basis. Thereafter, antibody screening and molecular phenotyping will be performed by a central lab at one month, three months, six months, nine months, 12 months, and 24 months. Antibody status, including HLA-DSA isotype and C1q-binding DSA status, will also be recorded when measured locally during the course of clinical care.

For central laboratory analysis, initial FlowPRA[®] (One Lambda, Canoga Park, CA) screening will be used to test for the presence of anti-HLA antibodies. Once identified, single antigen testing will be used to identify DSA specificity with an MFI greater than or approaching 1000 used to determine antibody positivity. For borderline cases, a three member adjudication panel of independent, qualified, HLA Lab Directors will determine positivity based on relevant clinical data. In samples that meet threshold criteria for DSA positivity, additional classification will be performed to determine the degree of antibody strength. By performing a single dilution (1:16) of DSA-containing samples, the alloimmune response can be further elucidated. Samples in which MFI disappears (becomes < 1000 MFI) will be regarded as "weak." Samples increasing to > 10,000 MFI upon dilution will be regarded as having significant prozone and will be regarded as "strong." Samples which may increase or decrease, but nevertheless remain between 1000 and 10,000 MFI will be regarded as "moderate." In certain cases, samples with evidence of fluorescence that are nevertheless below MFI criteria for DSA positivity will also be subject to dilution. Samples increasing to above threshold criteria following dilution will be regarded as positive and assumed to be under the influence of a prozone effect that impairs antibody detection. For statistical purposes, the DSA with the highest MFI level obtained during the course of the study will be used for statistical comparisons of DSA positivity between groups. However, the strongest antibody observed at each HLA-locus will be reported separately and tracked for subjects who are DSA positive. In all cases, positive DSA and/or molecular testing results will be

communicated to the subject's treating physician when available (DSA) or at the end of study (molecular testing). Testing will be performed in batches. De-identified typing reports (donor and recipient) will be requested from the participating centers to inform the central laboratory testing. De-identified results of recent local pre-transplant DSA testing (if performed per standard of care [SoC]) will also be requested to facilitate interpretation of central DSA testing results.

Follow-up visits will be performed quarterly during the first year of follow-up to collect standard clinical data. For follow-up beyond the first year, urinary protein, and tacrolimus trough concentrations obtained closest to targeted date of visit, per SoC, should be recorded. Up to two serum creatinine levels obtained at least one month apart, if performed per SoC, should also be recorded. Additionally, all local kidney biopsy results, AEs, and concomitant medications pertaining to AEs will be recorded. If the study progresses to two years, at the terminal study visit at 24 months, the most recently obtained lab results as well as any episodes of rejection, need for antibody reduction, graft loss, and deaths occurring beyond the first year will be detailed in the electronic Case Report Form (eCRF). Final testing for DSA and molecular profiling will also be performed at the 24 month visit.

Pathology results [hematoxylin and eosin (H&E), light microscopy, and immunofluorescence] will be appended to the eCRF when local kidney biopsies are performed and interpreted during the course of clinical care. De-identified copies of all kidney pathology reports must be submitted to Astellas. For all participants who undergo at least one kidney biopsy during the first year post-transplant (either for cause or per institutional protocol), the kidney biopsy performed closest to the 12 month visit (but no later than 14 months post-transplant) will be submitted for central pathological grading. All biopsies that are submitted for central pathology review will be evaluated and scored using the most recent version of the 2007 Update to the Banff '97 Classification by a central pathologist blinded to clinical results and subject identifiers.

3.3 Randomization

Randomization will be carried out using permuted blocks. The randomization allocation will consist of a 1:1 ratio for twice daily, immediate-release tacrolimus or Astagraf XL. The randomization will be stratified according to the following three factors:

- Planned use of alemtuzumab (Campath) (yes/no)
- Kidney donor profile index (KDPI) [three levels: N/A (living donors) vs. $\leq 50\%$ vs. $> 50\%$]
- HLA Class II mismatch (yes/no)

Additionally, enrollment of Campath users will be capped to not exceed 20% of the study population.

Subjects enrolled will be randomized using one central list via Interactive Response Technology (IRT). Prior to the initiation of the study treatment, the site staff will contact the IRT in order to determine the randomly assigned treatment. Specific procedures for randomization through the IRT are contained in the study procedures manual. Each subject

will be assigned a randomization number that is five digits long. The first two digits are chosen to be fixed for each strata; and the last three digits correspond to the sequential subject number (001 to 550) for the study subjects in each strata.

4 SAMPLE SIZE

The sample size for this study was determined based upon a comparison of the rate of the two-part composite endpoint in the Astagraf XL group compared to the immediate-release tacrolimus group. Assuming a rate of 20% would be observed for the immediate-release tacrolimus group compared to a rate of 10% for the Astagraf XL group, 220 subjects per group are needed to achieve an 80% power to detect a difference between Astagraf XL and immediate-release tacrolimus with a two-sided alpha level of 0.05. The study will enroll 275 subjects/group (550 total) to allow for 20% dropout.

5 ANALYSIS SETS

In accordance with International Conference on Harmonization (ICH) recommendations in guidelines E3 and E9, the following analysis sets will be used for the analyses.

Detailed criteria for analysis sets will be laid out in Analysis Dataset Specifications and the allocation of subjects to analysis sets will be finalized prior to database hard lock.

5.1 Full Analysis Set (FAS)

The full analysis set (FAS) will consist of all subjects who are randomized and receive at least one dose of study drug (Astagraf XL or immediate-release tacrolimus). Subjects will be included in the FAS based on randomized study drug assignment. This population will be used for selected demographic and baseline summaries and for sensitivity analysis of primary efficacy endpoint.

5.2 Modified Full Analysis Set (mFAS)

The modified full analysis set (mFAS) consists of all subjects who are randomized and received at least one dose of study drug (Astagraf XL or immediate-release tacrolimus), and whose pre-transplant cross-match antibody samples do not demonstrate pre-formed DSA for the duration of the study. This will be the primary analysis set for efficacy assessments, and subjects will be included based on randomized study drug assignment.

The selection of subjects for the mFAS will be confirmed in the Analysis Set Classification Meeting (ASCM) / Data Review Meeting.

The mFAS will be used for summaries and primary analyses of efficacy data, as well as selected demographic and baseline characteristics.

5.3 Per Protocol Set (PPS)

The Per-Protocol Set (PPS) includes all subjects of the mFAS who do not experience any protocol deviation criteria defined in Section 7.2.2.

Final judgments on exclusion of subjects from the PPS will be made at the ASCM and data review meeting, held prior to database lock.

The PPS will be used for secondary analyses of efficacy data.

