5 TREATMENTS AND EVALUATION

5.1 Dosing and Administration of Study Drug(s) and Other Medication(s)

5.1.1 Dose/Dose Regimen and Administration Period

Study participants will receive either Astagraf XL (single daily dose) or SOC, twice daily, immediate-release tacrolimus for up to 730 consecutive days (2 years) following their transplant procedure. Investigators are encouraged to start subjects on the randomized study treatment (immediate release tacrolimus or Astagraf XL) within 48 hours of transplantation. If medically indicated, therapy initiation with either tacrolimus agent can be delayed for up to 7 days. Administration of the randomized study treatment prior to the transplant is not allowed for the purposes of the current study.

When possible, patients should receive their daily dose of Astagraf XL using the fewest number of pills possible (i.e., a patient on 15 mg of Astagraf XL daily should ideally receive three 5 mg tablets). **Because of its extended-release pharmacokinetics, it is critical that Astagraf XL be initiated at a dose of 0.15/mg/kg/day as a single daily dose.** Failure to

dose patients in this manner will result in a protocol violation. Dry weight (or estimated dry weight, if dry weight is not available) should be used for the initial dosing. There is no dosing adjustment for subjects with gastric sleeves. After the initial dose, Astagraf XL dosing should be titrated according to the clinical judgment of the attending physician and appropriate TDM of tacrolimus trough concentrations, typically occurring 48 hours after a dose change. This dosing should account for the fact that when identical trough levels are targeted, systemic exposure to tacrolimus is the same for both Prograf and Astagraf XL.

Patients receiving immediate-release tacrolimus should be initiated on therapy per center protocol.

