7.2.3 Per Protocol Set (PPS)

The per protocol set will consist of the subset of the FAS who do not experience any major protocol deviations. Final adjudication and assessment of the classification for any protocol deviations will be conducted prior to database hard-lock. Further criteria may be defined in the SAP.

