7.2.2 Protocol Deviations

Protocol deviations as defined in the study protocol (Section 8.1.6 Protocol Deviations) will be assessed for all randomized subjects. The number and percentage of subjects with major protocol deviations will be summarized by criterion, (randomized) treatment group, and overall. Protocol deviations will also be summarized by study site. Subjects with more than one major deviation from the same criterion will be summarized once for the corresponding criterion. Any subjects who have more than one major deviation will be counted once in the overall summary. A data listing will be provided for all deviations by site and subject.

All deviations will be assessed as either major or minor according to a final review meeting prior to unblinding.

The protocol deviation criteria will be uniquely identified in the summary table and listing. The unique identifiers will be as follows:

- PD1 - Entered into the study even though they did not satisfy entry criteria,
- PD2 - Developed withdrawal criteria during the study and was not withdrawn,
- PD3 - Received wrong treatment or incorrect dose,
- PD4 - Received excluded concomitant treatment.

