8 DOCUMENT REVISION HISTORY

Version	Date	Changes	Comment/rationale for change
1.00	12-JUL-2018	NA	NA
2.00	25-OCT-2019	1. Define a biopsy set	To facilitate analyses of biopsy based endpoints by selecting subjects who undergo at least one kidney biopsy.
		2. Define protocol deviation based on ICH guidance. Clarify PPS definition.	To follow ICH guidance on defining protocol deviations and a PPS. PPS is further clarified as subjects of the mFAS who do not experience any protocol deviation criteria defined in Section 7.2.2. This will allow for a more meaningful comparison of the results between mFAS and PPS since mFAS is the analysis set for primary efficacy analyses.
		3. Revise the plan for risk factor analysis	To prevent from overfitting of logistic regression models when the expected number of incidences is very small. A large number of pre-specified risk factors and predictors can potentially affect accuracy of the estimated parameters in the case of low event rates.
		4. Define prior medication	To be more clinically relevant, previous medication is defined as medications which started and stopped prior to transplant.
		5. Time-to-first occurrence for DSA, HLA-DQ DSA, C11-binding DSA, DSA IgG ₃ type, IA, TG, etc.	When it is not possible to define the exact date of occurrence due to the way the data is collected, the analysis of time-to-first occurrence cannot provide exact information.
		6. Revise the analysis of tacrolimus dose and trough concentration	To provide clarification and details.
		7. Revise the analysis of plasma exchange therapy	Given that the low number of incidence is expected, assessing the treatment differences are not practically applicable. Descriptive statistics will be summarized.
		8. Add the estimation exposure-adjusted incidence rate (EAIR) for TEAEs and SAEs in the safety analysis plan	The crude percent estimation of AEs can result in the increased percent rates for TEAEs and SAE particularly in the later phase of the study.
		9. Exploratory endpoints and analyses	The exploratory endpoints and analyses have been adjusted based on available data, to more closely address the clinical and research questions.

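### SAP 5.3 omits the protocol's limit to major deviations, so the per-protocol set can lose patients unequally by arm through the Astagraf XL starting-dose rule

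*SAP*

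**What the plan says.** The two documents define the per-protocol set differently. Protocol 7.2.3: "The per protocol set will consist of the subset of the FAS who do not experience any major protocol deviations". SAP 5.3: the set "includes all subjects of the mFAS who do not experience any protocol deviation criteria defined in Section 7.2.2". The SAP revision history (Section 8, version 2.00, item 2) repeats the SAP form: "PPS is further clarified as subjects of the mFAS who do not experience any protocol deviation criteria defined in Section 7.2.2".

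SAP 7.2.2 lists four criteria: entry criteria not met (PD1), a withdrawal criterion met without withdrawal (PD2), "PD3 - Received wrong treatment or incorrect dose", and excluded concomitant treatment (PD4). The same section has every deviation graded major or minor at a final review meeting and tabulates the major ones. SAP 5.3 also leaves the final judgment on PPS exclusions to the analysis set classification and data review meeting before lock.

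Protocol 5.1.1 fixes a weight-based single daily starting dose for Astagraf XL and says that failure to "dose patients in this manner will result in a protocol violation". For the comparator the same section says: "Patients receiving immediate-release tacrolimus should be initiated on therapy per center protocol".

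Under SAP 7.4 and 7.4.1.2 the PPS is used for a secondary analysis of the primary endpoint and for a second run of the risk-factor models. The primary analysis uses the mFAS.

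**The concern.** A minor deviation is enough to leave the PPS under the SAP but not under the protocol. The SAP creates the grading that would separate the two cases and then does not use it to define the set.

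This matters more than a wording mismatch usually would because one kind of deviation is tied to one arm. The protocol gives a number against which an Astagraf XL starting dose can be judged, and it gives none for immediate-release tacrolimus. If a starting-dose violation is coded as an incorrect dose under PD3, every such patient, however small the departure, leaves the Astagraf XL side of the PPS, with no equivalent fixed-dose test on the control side. Patients started off the planned dose may differ in risk from the rest, so the PPS contrast could shift without any treatment effect. The revision history says the sponsor wants a more meaningful comparison of mFAS and PPS results. Arm-dependent removal would make that comparison harder to interpret.

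**Working it through.** **1. The two rules side by side**

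| | Protocol 7.2.3 | SAP 5.3 |
|---|---|---|
| Starting set | FAS | mFAS |
| Removed for | major deviations | any PD1–PD4 criterion |
| Uses the major/minor grade | yes | no |

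The revision-history rationale, that the mFAS is the primary efficacy set, explains the change of starting set. It gives no reason for removing subjects whose deviation is graded minor.

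**2. Which criteria can fall unequally by arm**

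PD1, PD2, PD4 and the wrong-treatment half of PD3 apply to both arms. The incorrect-dose half of PD3 is not restricted to one arm by its wording, but only Astagraf XL has a protocol-stated starting dose. A control patient could be coded only against a center protocol, for which the trial documents give no value.

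**3. The plan's own figure**

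The documents give no PPS size and no deviation rate. The only figure that can be checked is the sample size in Protocol 7.1 and SAP 4: 20% against 10%, two-sided 0.05, 80% power, 220 per group. The two-proportion formula with continuity correction gives 219 (199 without correction). Fisher exact power at 220 per group is 81.1%. Enrollment is 220/(1 − 0.20) = 275 per group. The stated figures reproduce, and 220 per arm is the base below.

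**4. Illustration: no true difference, removed patients at higher risk**

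Assumptions (none from the documents except the 20% rate and the 220): both arms have a true rate of 20%; a fraction x of the Astagraf XL arm only is removed; removed patients have k times the event rate of those kept.

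Kept rate r = 0.20 / [(1 − x) + kx]. PPS odds ratio = [r/(1 − r)] / (0.20/0.80). The rejection rate is two-sided at 0.05, by normal approximation with unpooled variance, for 220 against 220(1 − x).

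| k | x | r | PPS odds ratio | Rejection rate |
|---|---|---|---|---|
| 1.5 | 10% | 0.20/1.05 = 0.190 | 0.94 | 5.7% |
| 1.5 | 20% | 0.20/1.10 = 0.182 | 0.89 | 7.4% |
| 1.5 | 30% | 0.20/1.15 = 0.174 | 0.84 | 9.8% |
| 2 | 20% | 0.20/1.20 = 0.167 | 0.80 | 13.7% |

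**5. The same removal with lower-risk patients**

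If the removed patients have a 10% event rate, r = (0.20 − 0.10x)/(1 − x).

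| x | r | PPS odds ratio |
|---|---|---|
| 10% | 0.19/0.90 = 0.211 | 1.07 |
| 20% | 0.18/0.80 = 0.225 | 1.16 |
| 30% | 0.17/0.70 = 0.243 | 1.28 |

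The direction therefore depends entirely on who is removed.

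**6. Removal unrelated to outcome**

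For 20% against 10%, power by the uncorrected formula falls from 83.8% with no removal to 81.6% at x = 10% and 75.3% at x = 30%. At modest removal the loss of numbers matters little. The issue is possible bias.

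**The case against.** The case for the SAP as written has real content.

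- **The SAP may refine the PPS.** Protocol 7.2.3 adds: "Further criteria may be defined in the SAP". The change is also disclosed in the revision history, and PD1–PD4 are the categories that Protocol 8.1.6 requires sites to report to the sponsor, not an open list of trivial departures. This stands as far as permission goes. It does not explain why a deviation graded minor should exclude a subject.
- **Exclusion is not mechanical.** The classification meeting has the final say. This stands, but no criterion is given for its judgment, and the SAP's promise to grade before unblinding offers limited protection in an open-label trial.
- **The link to PD3 is inferred.** No passage says that a starting-dose violation is coded PD3. It is the natural reading, and no more than that.
- **Any imbalance would be seen.** SAP 7.2.1 already reports PPS exclusions by reason and treatment group. This stands, so no new table is needed. The table shows an imbalance but does not prevent it.

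A reader might infer four stronger things that the documents do not support. The first is that the PPS as a whole removes patients from one arm only; most criteria apply to both. The second is that almost every Astagraf XL patient would be in breach because capsule strengths rarely match a weight-based dose exactly. Protocol 5.1.1 accepts an estimated dry weight and asks for the fewest pills, which does not suggest exact enforcement. The third is that the bias favors Astagraf XL; step 5 shows that it can go the other way. The fourth is that starting-dose deviations should never exclude anyone. That is a debatable choice for a per-protocol set, given that the protocol calls this dose critical.

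**Conclusion.** The point holds in a limited form. SAP 5.3 and Protocol 7.2.3 disagree on whether a minor deviation removes a subject, and the SAP's own grading is left unused. Taken literally, and if starting-dose violations are coded under PD3, the rule can thin the Astagraf XL arm differentially through that one criterion.

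The size and direction of the effect cannot be stated from the documents. The odds ratios of 0.94 to 0.84 and the reverse case of 1.07 to 1.28 show what assumed removal of 10% to 30% would do under assumed event rates; they are not estimates for this trial.

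The primary analysis is untouched. The exposure is limited to the PPS analysis of the primary endpoint and the PPS risk-factor models, in a trial that describes itself as exploratory. The correction is worth making because it is cheap and settles who enters the set. No view is taken on the starting dose itself.

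**What to change.** In SAP 5.3, limit exclusion to mFAS subjects with a *major* deviation under one of the Section 7.2.2 criteria, and align item 2 of the revision history.

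In SAP 7.2.2, have reviewers masked to outcome set, before lock, a written rule for when an incorrect dose under PD3 is major. The rule should be phrased so that it can be applied in either arm and so that a minor starting-dose departure does not by itself remove a subject.

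Read the PPS result beside the exclusions by reason and arm already planned in SAP 7.2.1.

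The cost is a wording change, a short grading rule and a re-derived PPS flag. The downside is that some subjects with minor deviations stay in the PPS.
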